## **9 Trial Objectives**

### **9.1 Primary Objective**

The primary objective is to evaluate the safety of once daily use of calcipotriol (50 mcg/g) plus betamethasone (0.5 mg/g) (as dipropionate) gel in adolescent subjects (aged 12 to 16 years, 11 months) with scalp and body psoriasis.

### **9.2 Secondary Objectives**

The secondary objective is to evaluate the efficacy of once daily use of calcipotriol (50 mcg/g) plus betamethasone (0.5 mg/g) (as dipropionate) gel in adolescent subjects (aged 12 to 16 years, 11 months) with scalp and body psoriasis.

## **10 Investigational Plan**

### **10.1 Trial Design**

This will be an international, multi-centre, prospective, non-controlled, open, single-group, 8-week trial in adolescent subjects (aged 12 to 16 years, 11 months) with scalp and body psoriasis.

The subjects will receive topical treatment with calcipotriol 50 mcg/g plus betamethasone 0.5 mg/g (as dipropionate) gel once daily for up to 8 weeks.

#### Washout/Screening Period

Depending on the prior use of disallowed treatments, the washout/screening period will last for 7 to 56 days prior to the first administration of LEO 80185 gel (Visit 1).

Prior to attending any study procedure, a signed informed consent must be obtained from the parent(s)/legal guardian(s) of the subject, or by the subject (as appropriate and according to national laws and regulations). Written assent should also be obtained from the subject. There are two screening visits: Screening visit 1 (SV1) and screening Visit 2 (SV2). Depending on the subjects' use of excluded treatments, SV1 is performed up to 7 weeks before SV2; SV2 is performed at 3 to 7 days before Visit 1.

#### Treatment Period

The treatment period will last for up to 8 weeks. There are up to 5 visits: Visit 1 (day 0), Visit 2 (day 14), Visit 3 (day 28), Visit 4 (day 42) and Visit 5 (day 56). Visits 2-5 should be performed within  $\pm 2$  days of the scheduled time relative to Visit 1; if they are outside this window, the (sub)investigator should record the reason in the subject's medical record.

LEO 80185 gel will be applied once daily to scalp psoriasis lesions. Subjects should be instructed to discontinue treatment on individual lesions if/when a lesion has cleared. Subjects whose psoriasis clears after 4-week treatment will stop the investigational product and leave the trial.

Subjects who have psoriasis after 4 weeks of treatment will continue treatment for another 4-week period.

Subjects whose psoriasis clears at Visit 2 or Visit 4 according to the (sub)investigator should discontinue treatment but will stay in the study. During periods of discontinuation of treatment the subject should restart the treatment if psoriasis reappears.

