**Methodology:**

An international, multi-centre, prospective, non-controlled, open, single-group, 8-week trial in adolescent subjects (aged 12 to 16 years, 11 months) with scalp and body psoriasis

Psoriatic lesions on the scalp and body will be treated with calcipotriol (50 mcg/g) plus betamethasone (0.5 mg/g) (as dipropionate) gel applied once daily for up to 8 weeks under maximal use conditions on the body.

The duration of the trial for each subject will be a maximum of 20 weeks, consisting of a screening period of 7 days to 8 weeks followed by a 4- or 8-week treatment period and, if required, a 2-4-week follow-up period.

Prior to Visit 1 (Day 0), a wash-out period (up to 8 weeks) should be completed if the subject is being treated or has recently been treated with anti-psoriatic treatments or other relevant medication, as defined by the exclusion criteria.

During the trial, the subset of subjects performing HPA axis assessments will be allowed to use non-steroid topical treatments without expected systemic effects to treat psoriasis lesions on the face and sensitive areas (armpits, groin, under the breasts and in other skin folds around the genitals and buttocks). Subjects not performing HPA axis assessments will be allowed to use any topical treatment

allowed except potent or very potent (WHO groups III-IV) corticosteroids to treat psoriasis lesions on the face and skin folds. Bath oils and moisturizing soaps are allowed. Topical vitamin D analogues (calcipotriol, calcitriol or tacalcitol) are limited to a maximum of 50 g, 75 g or 100 g of ointment/gel/cream per week depending on the subject's age and body surface area (BSA). This includes the amount of investigational product used.

The study will consist of a wash-out period (if required), 2 screening visits; SV1 and SV2 (to be conducted within 8 and 1 weeks prior to Visit 1, respectively) followed by a 4-or 8-week treatment period (Days 0-56). Subjects whose psoriasis is clear after 4-week treatment will stop the investigational product and leave the trial. Subjects who have signs of psoriasis after 4 weeks of treatment will continue treatment for another 4-week period. During the treatment period, the study visits will be on Days 0, 14, 28, 42 and 56 (Visits 1 to 5).

Each subject will receive the investigational product and will be instructed to apply it once daily.

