In the two trials MBL 0801 and MBL 0412 INT, no cases of hypercalcaemia and no clinically relevant changes in urinary calcium were reported. The adrenal response to ACTH challenge was measured in 30 patients; one patient showed a decrease in cortisol response to ACTH challenge after 4 weeks of treatment which was considered to be mild (7) (8).

In the present study LEO 80185 gel will be applied to lesions on both scalp and body. The risk of adrenal suppression with LEO 80185 gel is expected to be low with LEO 80185 being applied under maximal use conditions as systemic exposure is known to be low and the drug concentration is expected to be below the limit of quantification (Investigator's Brochure).

Subjects participating in the present study will perform ACTH-challenge test before and after treatment. The pre-treatment test is to ensure that adrenal function is normal before starting investigational product. Serum cortisol concentrations at 30 and 60 minutes after injection will be measured in order to show the maximum cortisol level achieved (26).

Overdosage with topical calcipotriol can cause hypercalcemia (27), due to the systemic absorption of calcipotriol, which then affects calcium metabolism as it is a vitamin D analogue. However, extensive experience with topical use of calcipotriol in psoriasis has demonstrated no significant impact on calcium metabolism when used in the recommended amounts (maximum weekly dose in adults of 100 g of a 50 mcg/g concentration). Doses up to 300 g have been used with serum calcium remaining within the normal range (29).

Two studies with calcipotriol ointment have been conducted in children 2-14 years of age and did not show effects on calcium metabolism (30) (31). One trial with Daivobet® Ointment, MCB 0501 INT, has been conducted in adolescent subjects and did not show any effects on calcium or HPA axis.

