The combination of high calcium intake with vitamin D supplementation, or extreme calcium intake alone, has been shown to significantly increase urinary calcium in adults (36). Hence, the use of calcium or vitamin D supplements will be excluded in this study.

Subjects will apply the LEO 80185 gel once daily for up to 8 weeks. This application frequency and treatment duration has been shown to be safe and effective in adults with 55-70% of subjects achieving controlled disease after 4-week treatment (37) (38). Only subjects who have signs of scalp and/or body psoriasis after 4 weeks of treatment will continue treatment in the study. As the application area and the amount of investigational product required is expected to decrease with time as lesions heal, continued treatment for up to 8 weeks is expected to be safe in those subjects who need it.

The maximum weekly dosage approved for adults is 100 g. In the present trial, the maximum weekly dose will be determined by age and BSA at baseline. For subjects aged 12 to 14 years with a BSA  $\leq 1.3 \text{ m}^2$ , the maximum weekly dosage will be 50 g of LEO 80185 gel per week. For subjects aged 12 to 14 years with a BSA  $> 1.3 \text{ m}^2$  and subjects aged 15 to 16 years, 11 months with a BSA  $\leq 1.7 \text{ m}^2$ , the maximum weekly dosage will be 75 g of LEO 80185 gel per week. For subjects aged 15 to 16 years, 11 months with a BSA  $> 1.7 \text{ m}^2$ , the maximum weekly dosage will be 100 g of LEO 80185 gel per week.

To be eligible for the study, all subjects are to have an extent of scalp and body (trunk and /or limbs) psoriasis of 10-35% BSA. In addition, subjects performing HPA axis assessments are to have an extent of scalp psoriasis that is more than or equal to 20% of the scalp area. Subjects not performing HPA axis assessments are to have an extent of scalp psoriasis that is more than or equal to 10% of the scalp area. The disease severity of body psoriasis and scalp psoriasis is to at least moderate according to the investigator's global assessment. It is expected that many adolescent subjects with psoriasis will have less extensive and less severe disease. However, since the main purpose of the present study is to evaluate the safety of the investigational product, the exposure to treatment has to be as close to maximum as possible.

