### **Investigator’s Assessment of the Extent of Psoriasis Vulgaris**

In order to obtain baseline data of psoriatic severity for all the subjects enrolled in the trial, the (sub)investigator will also assess the extent of the subject’s total psoriatic involvement at SV2 and Visit 1.

The total psoriatic involvement (e.g., the arms, the legs, the trunk, the scalp and the face) will be recorded as a percentage of the total BSA, estimating that the surface of the subject’s full, flat palm (including the five fingers) correlates to approximately 1% of the BSA.

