**Investigator's Assessment of the Extent of Scalp Psoriasis**

A baseline assessment of the extent of scalp psoriasis as percentage of the total scalp area will be done at SV2 and Visit 1, estimating that the surface of the subject's full, flat palm (including the five fingers) correlates to approximately 25% of the scalp area.

**Investigator's assessment of the extent and severity of clinical signs of psoriasis vulgaris (Redness, Thickness, Scaliness)**

At SV2 and Visits 1 to 5 and early withdrawal (if applicable), the (sub) investigator will make assessments of the extent and severity of clinical signs of the subject's psoriasis on specific areas of the body in terms of three clinical signs: redness, thickness and scaliness.

The **extent** of psoriatic involvement will be recorded for each of the four areas: head\*, arms\*\*, trunk\*\*\* and legs\*\*\*\* using the following scale:

- 0 = no involvement
- 1 = < 10%
- 2 = 10 - 29%
- 3 = 30 - 49%
- 4 = 50 - 69%
- 5 = 70 - 89%
- 6 = 90 - 100%

\*) head includes the neck

\*\*) arms include hands

\*\*\*) trunk includes flexures

\*\*\*\*) legs include buttocks and feet

The **severity** of the psoriatic lesions in each of the four areas will be recorded for each of the signs of redness, thickness and scaliness. For each clinical sign, a single score, reflecting the average severity of all psoriatic lesions on the given body region, will be determined according to the scale below:

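### Protocol Section 10.1 names scalp lesions as the application site and omits the body, in conflict with the synopsis and Section 8.3

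*Protocol*

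**What the plan says.** Three Protocol passages bear directly on where the gel is applied, and they differ.

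- **Synopsis, Methodology:** "Psoriatic lesions on the scalp and body will be treated with calcipotriol" plus betamethasone gel, "applied once daily for up to 8 weeks under maximal use conditions on the body".
- **Section 8.3, Trial Rationale:** "In the present study LEO 80185 gel will be applied to lesions on both scalp and body". The section adds that, since safety is the main purpose, "the exposure to treatment has to be as close to maximum as possible". It also reports a regulatory requirement to study the HPA axis and pharmacokinetics under maximal use in at least 30 patients.
- **Section 10.1, Treatment Period:** "LEO 80185 gel will be applied once daily to scalp psoriasis lesions". The body is not named.

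The opening of Section 10.1 gives no application site. Section 10.6.4.1 gives route, frequency, weekly maximum and number of bottles, but no area. It refers to an instruction sheet handed over at Visit 1, whose content is not in the documents.

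**The concern.** Section 10.1 is operative text that a site would consult to see what subjects do, so an omission there carries more weight than one in the background sections. Read literally, it leaves trunk and limb lesions without the gel. Section 10.6.10 allows no other anti-psoriatic treatment on the trunk and limbs, so those lesions would have no active treatment.

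The primary criteria include the cortisol response to ACTH, albumin-corrected serum calcium and 24-hour urinary calcium, all read as consequences of systemic absorption. Treating less skin would push them towards no effect. The efficacy criteria in Section 10.10.1 are body IGA, PASI and the patient's global assessment on the body, and these would be pushed towards failure. In the PASI formula of Section 10.8.3.1 the head carries weight 0.1, against 0.2 + 0.3 + 0.4 = 0.9 for arms, trunk and legs.

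The trial has one arm, so a shortfall in exposure would not show as a difference between groups. The HPA subset is also small. SAP Table 3 lists 31 cortisol results at 30 minutes at Week 4 and 29 at Week 8, so one subject is worth 1/31 = 3.2 or 1/29 = 3.4 percentage points.

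**Working it through.** **Inputs.** Section 10.8.3.1 gives two palm rules: one palm "correlates to approximately 1% of the BSA" and "correlates to approximately 25% of the scalp area". Inclusion criterion 7a (Section 10.4.1.1) sets an extent of 10 to 35% BSA, which Section 8.3 describes as covering scalp and body together. The scalp minimum is 20% of the scalp for HPA subjects (Section 10.4.1.2) and 10% for the others (Section 10.4.1.3). SAP Table 1 records a later body criterion of at least 3% BSA for subjects not performing HPA and PK assessments, with the scalp minimum kept at 10%.

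**Scalp as a share of BSA.** 1% / 0.25 = 4% BSA for the whole scalp.

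**Untreated share if only scalp lesions receive gel.** Let f be the fraction of scalp involved and E the total qualifying extent in % BSA. The untreated share is 1 - 4f/E. Under the later criterion body extent b is counted separately, so the share is b/(b + 4f).

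| Case | Calculation | Untreated |
|---|---|---|
| E = 10, whole scalp | 1 - 4/10 | 60% |
| E = 10, f = 0.2 (HPA minimum) | 1 - 0.8/10 | 92% |
| E = 10, f = 0.1 (non-HPA minimum) | 1 - 0.4/10 | 96% |
| E = 35, whole scalp | 1 - 4/35 | 89% |
| E = 35, f = 0.2 | 1 - 0.8/35 | 98% |
| E = 35, f = 0.1 | 1 - 0.4/35 | 99% |
| Later criterion, b = 3, whole scalp | 3/7 | 43% |
| Later criterion, b = 3, f = 0.1 | 3/3.4 | 88% |

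Under the 10-35% criterion the untreated share runs from 60% to 99%; at the HPA scalp minimum it is 92% to 98%. Under the later non-HPA criterion it starts at 43% and rises with more body disease.

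**Would the analysis show it?** SAP Section 6.1.1 defines compliance by days missed, so daily application to the scalp alone counts as full compliance. The per protocol exclusions in Protocol Section 10.11.1 concern applying no product, adrenal function at baseline and absence of post-treatment ACTH results; none concerns treated area. Bottle weights (SAP Section 6.4.2) measure grams, not site.

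The Protocol states no figure that depends on this sentence. Its precision statements in Section 10.3 are unaffected.

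**The case against.** The strongest reply is that no site reading the whole protocol would treat the scalp alone. The sentence does not say only, and the same paragraph goes on to speak of individual lesions and of psoriasis clearing, without limiting either to the scalp. Other text presupposes use on the body:

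- Inclusion criterion 7c-f requires scalp and body disease that can be treated within the weekly maximum of product.
- Exclusion criterion 9 refers to treated areas on the scalp or body.
- Section 10.6.10 forbids any *other* treatment on trunk and limbs.
- Sections 10.8.5.1 and 10.11.5.1 define adverse events by distance from treated lesions, allow trunk and limbs as a location and tabulate such events on the body.

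This stands. It makes a drafting omission the likely explanation, though that remains an inference.

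A reader might infer more: that the trial directed scalp-only treatment, or that subjects were under-exposed. The documents support neither. What families were told is on a sheet that is not included. The SAP cites protocol versions 4.0 and 6.0, while the supplied protocol carries the earlier entry criteria, so a later correction cannot be ruled out.

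Nor can the area shares be turned into dose. Earlier adolescent scalp trials report use of up to 69 g/week (Section 5.3), above the lowest weekly maximum here (50 g) and below the others (75 g and 100 g). Bottle weights might expose gross under-use, but a low weight could equally reflect limited or cleared disease.

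None of this removes the conflict between Section 10.1 and the synopsis and Section 8.3.

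**Conclusion.** The inconsistency is real and lies in operative text. It is not evidence of a design decision or of actual under-exposure. The consequence is conditional on a site or instruction sheet having followed Section 10.1 literally. In that case most of the qualifying lesion area would be untreated for every subject under the 10-35% criterion, and for nearly all, though not every possible subject, under the later non-HPA criterion. The synopsis condition of maximal use on the body would not be met, because no body area would be treated.

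The sizes rest on the protocol's approximate palm rules and on the qualifying extent including scalp lesions. If the 10-35% were body disease alone, the smallest untreated share would be 10/14 = 71% rather than 60%. The directions of bias follow from treated area; their size in cortisol, calcium or response terms cannot be derived from the documents.

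**What to change.** Reconcile the Section 10.1 sentence with the synopsis and Section 8.3. State one application area in the same words in Sections 10.1 and 10.6.4.1 and on the treatment instruction sheet. Which area that is rests with the sponsor.

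Check the sheet actually used and the later protocol versions. If both agree with the synopsis and Section 8.3, record that in the trial report and the matter is closed. If any subjects were told to treat the scalp alone, identify them and report the HPA, calcium and body efficacy results with and without them. The SAP, dated 16-Mar-2018, was written after data review and places the analysis sets in a separate document, so a with-and-without presentation is more practical than redefining the sets.

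The cost is a short wording change, a document check and, if needed, a site query. Extra tables are needed only if affected subjects are found; no new procedures or data collection are required.

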#### Follow-up

If applicable, the treatment period will be followed by a follow-up (FU) period consisting of visit FU1 and/or visit FU2.

[figure not shown]
Visit FU1 will take place 14 days after the last visit in the treatment period, but only if there was an ongoing adverse event at this time of possible/probable/not assessable relationship to the investigational product. At the (sub)investigator's discretion, the information required at this visit may be obtained over the telephone, and the subject need not make the visit. FU1 should also be performed if albumin corrected serum calcium is *above* the reference range at the last on-site visit. A new blood sample should then be collected.

Visit FU2 will take place 28 days after the ACTH-challenge test performed at Visit 3 or Visit 5, but only if this test showed a serum cortisol concentration  $\leq 18$  mcg/dl at 30 minutes after ACTH-challenge.

Visits FU1 and FU2 should be performed within  $\pm 2$  days of the scheduled time; if they are outside this window, the qualified site staff person should record the reason in the subject's medical record/source document.

For details, see Section 10.8 for the schedule of trial procedures.

### 10.1.1 Overall Chart

There should be at least 4 days between SV1 and SV2 so dietary information (diary) can be collected.

### 10.2 Time Schedule

Planned date of enrolment of first subject: October 2013

Planned date of enrolment of last subject: August 2015

Planned date of completion of last subject: October 2015

### 10.3 Number of Subjects/Sample Size

Enrolment of subjects will continue until data from 100 subjects are available for evaluation of the effect of LEO 80185 on calcium metabolism (i.e. the measurement of the serum calcium concentration and the 24-hour urinary calcium excretion and/or the urinary calcium:creatinine ratio is available before and at Visit 3 and/or Visit 5). Therefore, the number of enrolled subjects can exceed 100 subjects.

The 100 subjects include the enrolment of 30 evaluable subjects in the U.S. without adrenal suppression at baseline who undergo the ACTH-challenge test at end of treatment (Visit 3 or Visit 5). At the time the sponsor confirms 30 evaluable subjects has been obtained, there may be other subjects ongoing in the trial that have not yet had the ACTH-challenge test. Such subjects will be allowed to complete the trial without the ACTH-challenge test.

The primary objective of the trial is to evaluate the safety of LEO 80185 gel. No formal sample size calculation evaluating the power of the trial has been performed. However, a few considerations regarding the sample size have been made as described below.

The upper limit of an exact two-sided 95% confidence interval for the probability of observing a specific adverse event, when 0 out of 100 possible events have been observed, is approximately 4% assuming a binomial distribution.

With 100 subjects and an assumed response rate (percentage of subjects who achieve “Clear” or “Almost clear” according to the investigator’s global assessment of disease severity on the body at end of treatment) of approximately 30%, the 95% confidence interval for the estimated response rate will be approximately  $\pm 9\%$ .

Each centre should aim to enroll a minimum of three subjects. As the subjects are anticipated to be difficult to recruit, the suggested minimum number of subjects per centre is based on practical considerations rather than statistical robustness of estimates given per centre.

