**Number of subjects to be enrolled:**

In total, a sufficient number of subjects will be enrolled to ensure 100 subjects are evaluable for calcium metabolism. Thirty of the 100 subjects will also be evaluable for HPA axis suppression. At least 30 subjects will be evaluable for pharmacokinetic evaluation.

In the U.S. only, subjects will perform hypothalamic-pituitary-adrenal (HPA) axis function assessments until 30 evaluable subjects are obtained.

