Calcium metabolism will be evaluated in the present study by 24-hour urinary collection and measurement of serum calcium, -phosphate and plasma PTH before, during and/or after treatment. 24-hour urine will be collected and the urinary calcium-, phosphate- and creatinine excretion will be measured and the calcium:creatinine and phosphate:creatinine ratios calculated. Subjects who report an incomplete 24-hour urinary collection will be excluded from the analyses of 24-hour urinary calcium and phosphate excretion but will still be analysed for calcium:creatinine and phosphate:creatinine. To identify any severe, non-reported sampling errors the daily creatinine excretion/kg body weight will be calculated as proposed by Remer et al. (32).

It is well established that there is a relationship between dietary calcium intake and the urinary calcium excretion in adults. However, in rapidly growing adolescents, it appears that only dietary calcium intake above a certain threshold of approximately 1500 mg/day will result in an increase in urinary calcium excretion (33). As this study includes adolescents 12 to 16 years, 11 months of age, some of the subjects may not be in phase of rapid growth and some subjects might consume large amounts of dairy products. Therefore, there is a possibility of an effect of the diet on the calcium excretion.

A review of the subject's normal diet will be done. As dairy products account for approximately 73% of the total dietary calcium content, and as the calcium from other sources such as vegetables and grains are less easily absorbed (34), the review will focus on the intake of dairy products. The subjects will be asked to keep a diary of the daily intake of dairy products and calcium-fortified products (e.g. bread, cereals, orange juice or soy milk). The number of daily servings of calcium defined as one cup (240 ml) or 1.5 ounces of cheese (43 g) in dairy products such as milk, yoghurt or cheese or of a calcium-fortified product with corresponding calcium content (300 mg calcium/cup) will be estimated (35). The subjects will be asked to keep the same number of daily servings three days prior to and during each 24-hour urine collection. The number of daily calcium servings should not exceed five (i.e. 1500 mg calcium).

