#### Urinalysis

The following will be analysed quantitatively in the collected 24 hour urine:

Calcium  
Phosphate  
Creatinine  
Volume

The following analyses will be performed on the spot urine sample by dipstick test:

Glucose  
Ketones

The laboratory will also report:

Albumin-corrected serum calcium in mmol/l using the formula:

$$\text{serum calcium (total) in mmol/l} + (0.02 \times [40\text{-serum albumin in g/l] )$$

For the 24 hour urine sample the following will be calculated:

Total calcium excretion  
Total phosphate excretion  
Total creatinine excretion  
Calcium: creatinine ratio  
Phosphate: creatinine ratio

If any laboratory results are abnormal, the (sub)investigator should follow-up the subject as clinically appropriate.

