### **10.11.7 General Principles**

Categorical data will be summarised using the number and percentage of subjects in each category. Continuous data will be summarised using the mean, standard deviation (SD), median, minimum and maximum values.

All confidence intervals will be two-sided and presented with 95% degree of confidence, unless otherwise stated.

The data recorded during the course of the trial will be presented in individual data listings, according to ICH E3.

For tabulations on changes from baseline, baseline will be defined as the last assessment performed before application of IP.

The end of treatment value for a particular parameter will be defined as the last value recorded for that parameter up to and including Visit 5 (Week 8). However, for laboratory parameters this will be the last value recorded after baseline (SV2) up to and including Visit 5.

All efficacy data will be tabulated by visit using an observed cases approach (i.e. involving only those subjects who attended each specific visit) except for the tabulation of end of treatment values.

All laboratory data will be tabulated by visit using an observed cases approach except for the tabulation of end of treatment values which will be presented for the primary response criteria.

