6.4.4 Laboratory Data

The laboratory data will be presented for the safety analysis set as described in the protocol.

However, 25-hydroxy vitamin D baseline values will not be summarized since no abnormal values have been observed.

The following approach will be used in case of repeated or missed laboratory measurements:

- if an initial measurement was normal but the measurement was still repeated then the initial measurement will be presented in the tables and both measurements will be included in the listing.
- if an initial measurement was repeated by mistake then the initial measurement will be presented in the tables and both measurements will be included in the listing.
- if an initial measurement was abnormal and the measurement was repeated due to a technical problem then the repeated measurement will be presented in the tables and both measurements will be included in the listing.
- if an initial measurement was missing but a measurement from an unscheduled visit is available and the unscheduled visit was performed within 5 days after the actual visit then the measurement from the unscheduled visit will be used, for example one measurement from an unscheduled visit after Visit 3 will be included in the analysis of albumin corrected serum calcium (gives a total of 100 measurements).

The number of measurements outside the reference range will be presented in relevant laboratory tables. The number of measurements for other than primary and secondary endpoints that fall outside the limit for quantification will be presented in relevant laboratory tables.

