Table 2-24 Patient's assessment of sleep loss by visit and at end of treatment: full analysis set

Trial ID: LP0076-1017	Date: 16-Mar-2018	Version: 1.0 Page 21 of 27
-----------------------	-------------------	-------------------------------

Table 2-25 Change in sleep loss from baseline to each visit and end of treatment: full analysis set

Tables and Figures, Safety Data (Module 4)

Tables

Table 3-1 Subjects with serum cortisol concentration ≤ 18 mcg/dL at 30 minutes after ACTH challenge at Week 4 and Week 8: per protocol analysis set

Table 3-2 Subjects with serum cortisol concentration ≤ 18 mcg/dL at both 30 and 60 minutes after ACTH challenge at Week 4 and Week 8: per protocol analysis set

Table 3-3 Serum cortisol concentration at time 0 and at 30 and 60 minutes after ACTH challenge at baseline, Week 4 and Week 8: per protocol analysis set

Table 3-4 Individual data for subjects with serum cortisol concentration ≤ 18 mcg/dL at either 30 minutes or 60 minutes after ACTH challenge: per protocol analysis set

Table 3-5 Change in albumin-corrected serum calcium from baseline to Week 4, Week 8 and end of treatment: safety analysis set

Table 3-6 Albumin-corrected serum calcium at baseline, Week 4, Week 8 and end of treatment: safety analysis set

Table 3-7 Albumin-corrected serum calcium categorised as low, normal or high at Week 4, Week 8 and end of treatment shown against baseline category: safety analysis set

Table 3-8 Change in 24-hour urinary calcium excretion from baseline to Week 4, Week 8 and end of treatment: safety analysis set

Table 3-9 24-hour urinary calcium excretion at baseline, Week 4, Week 8 and end of treatment: safety analysis set

Table 3-10 24-hour urinary calcium excretion categorised as low, normal or high at Week 4, Week 8 and end of treatment shown against baseline category: safety analysis set

Table 3-11 Change in 24-hour urinary calcium excretion from baseline to Week 4, Week 8 and end of treatment in subjects with complete urinary collection: safety analysis set

Trial ID: LP0076-1017	Date: 16-Mar-2018	Version: 1.0 Page 22 of 27
------------------------------	--------------------------	-------------------------------

Table 3-12 24-hour urinary calcium excretion at baseline, Week 4, Week 8 and end of treatment in subjects with complete urinary collection: safety analysis set

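### Does the SAP need to state how many subjects met the protocol's definition of evaluable for calcium metabolism?

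*Protocol*

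**What the plan says.** The synopsis promises that "a sufficient number of subjects will be enrolled to ensure 100 subjects are evaluable for calcium metabolism". Section 10.3 defines evaluable as a composite: "the measurement of the serum calcium concentration and the 24-hour urinary calcium excretion and/or the urinary calcium:creatinine ratio is available before" and again at Visit 3 and/or Visit 5. It adds that enrolment may exceed 100.

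Both urinary measures come from one specimen. Section 10.8.4.1 introduces total calcium excretion and the calcium:creatinine ratio together with "For the 24 hour urine sample the following will be calculated". Section 8.3 treats them differently in one case: subjects who report an incomplete collection "will be excluded from the analyses of 24-hour urinary calcium and phosphate excretion but will still be analysed for calcium:creatinine and phosphate:creatinine".

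The SAP gives availability by test and visit in section 6.5.2, Table 3. In section 6.4.4 it lets an unscheduled result replace a missing one if "the unscheduled visit was performed within 5 days after the actual visit then the measurement from the unscheduled visit will be used". Its example is one serum value taken after Visit 3, which "will be included in the analysis of albumin corrected serum calcium (gives a total of 100 measurements". Appendix I lists the resulting analyses by title, such as "Change in 24-hour urinary calcium excretion from baseline to Week 4, Week 8 and end of treatment: safety analysis set". Section 5 of the SAP refers the analysis sets to a separate Analysis Set Definition Document, which was not supplied.

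**The concern.** Protocol section 8.3 ties the 100 evaluable subjects to a post-marketing commitment to the FDA, so whether the number was reached is a fair question. The SAP was written with the data in view, yet it gives only separate counts for each test and visit. A reader who meets the figure 100 in SAP section 6.4.4 could take it as confirmation of the target. It is a count of one analyte at one visit, whereas the target needs serum and urine, before and after treatment.

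Table 3 then suggests a shortfall, because fewer than 100 subjects have either urinary measure at baseline.

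A second worry is the replacement rule. Under protocol section 10.1, SV2 falls 3 to 7 days before Visit 1. A replacement taken up to 5 days after SV2 could therefore fall up to 5 - 3 = 2 days after the first application and still be used as baseline.

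**Working it through.** **Inputs (SAP Table 3, subjects assigned to treatment)**

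| Measure | SV2 | Week 4 | Week 8 |
|---|---|---|---|
| Albumin-corrected serum calcium | 107/107 | 99/104 | 87/90 |
| 24-hour urinary calcium | 98/107 | 92/104 | 79/90 |
| Urinary calcium:creatinine ratio | 98/107 | 92/104 | 79/90 |

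**Stated figures.** Week 4 serum calcium: 99 + 1 unscheduled = 100, as SAP section 6.4.4 says. The precision statements in protocol section 10.3 also reproduce. The upper limit for 0/100 is 1 - 0.025^(1/100) = 3.62%, about 4%. The half-width at 30% is 1.96 × √(0.3 × 0.7/100) = 8.98%, about 9%. These concern adverse events and IGA response, so the calcium count does not enter them.

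**Ceiling for the composite.** If the same nine subjects lack both urinary measures at SV2, at most 107 - 9 = 98 can qualify. Week 4 or Week 8 data could cover all 98.

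**Floor.** With no overlap between missing serum and missing urine, at least 92 + 99 - 104 = 87 subjects have both at Week 4. Removing up to nine without baseline urine leaves 87 - 9 = 78, or 79 with the unscheduled serum value. Reaching 78 also requires everyone who fails at Week 4 to fail or be absent at Week 8. An integer programme over all availability patterns consistent with Table 3 gives the same limits: 78 to 98, or 79 to 98.

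**If the ceiling's condition fails.** Section 10.3 accepts either urinary measure. If different subjects lack the two measures, the Table 3 totals allow up to 104, the number in the Week 4 denominator. The common specimen and the identical counts at all three visits make this unlikely but do not exclude it.

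**Pairs for change in 24-hour urinary calcium**, before incomplete collections are removed: Week 4, 92 - 9 = 83 up to 92; end of treatment, 83 up to 98. These are the numbers the intervals will use whether or not a composite count is printed.

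**Size of the gap.** At 98, an interval for a mean is wider than at 100 by a factor of about √(100/98) = 1.01.

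**Baseline timing.** Protocol section 10.11.7 says "baseline will be defined as the last assessment performed before application of IP", and SAP sections 6.1 and 6.3 repeat the condition. A replacement urine taken after first application is therefore not a baseline value, whatever the 5-day rule allows. Neither document records an unscheduled baseline urine.

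**The case for a change.** The best case for a change is that the count is cheap, the data were in hand, a regulator asked for 100, and under the likely pattern of missing data even the best case is 98. For change in 24-hour urinary calcium, a primary criterion, the cap of 98 pairs does not depend on the ratio at all; it needs only that no pre-treatment unscheduled urine was recovered.

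The arithmetic in that argument stands, and so does the observation that these two documents do not let a reader confirm the target. The step to a defect in the plan does not:

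- The 100 is a rule for continuing enrolment. Protocol sections 10.11.1 and 10.11.5 analyse calcium on the safety analysis set, so no analysis uses a composite evaluable set.
- SAP section 6.4.4 already names both the analyte and Visit 3 for its 100 measurements. A careful reader is not misled.
- Table 3 shows 99 for Week 4 serum calcium where the analysis uses 100, so it omits at least one recovered value. The SAP gives that value only as an example, and urine values may have been recovered in the same way.
- The SAP works from protocol versions 4.0 and 6.0; the supplied protocol still has the eligibility criteria those versions replaced. The SAP's table of amendments shows no change to section 10.3, but it also omits serum alkaline phosphatase, which SAP Table 3 treats as a secondary endpoint and the supplied protocol does not mention. Its silence is weak evidence that the definition stayed the same.
- Appendix I gives table titles only, so nothing indicates that the paired numbers will be left out of the change tables.

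**Conclusion.** No change to the plan is needed. The missing count is a recruitment tally that the trial report, or the Analysis Set Definition Document, can supply from existing data. Printing it in the SAP would alter no estimate, interval or conclusion.

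The composite count is probably at most 98, two short of 100. That rests on three assumptions: the same nine subjects lack both baseline urinary measures, no pre-treatment unscheduled urine exists, and section 10.3 is unchanged in the final protocol. The figure of 78 is a mathematical limit and should not be read as an estimate. Relaxing the first assumption alone raises the limit to 104, so Table 3 does not by itself prove a shortfall. The worry about post-application baseline values is hypothetical and is already settled by the baseline definition in both documents.
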